1.15 Laboratory Procedures/Evaluations

Upon completion of extraction, the teeth will be placed in formalin-containing bottle. After formalin fixation, the teeth will be prepared for histological examination using 10% EDTA for demineralization. Following that, the teeth are trimmed, embedded in paraplast and cut longitudinally to obtain 6um thick section. The sections were stained with H&E and examined with a light microscope. The histological diagnosis are based on the classification used by Seltzer et al. as follow:

- 1. Normal Pulp: Intact, uninflamed pulp
- 2. Transitional Stage: Intact pulp with scattered inflammatory cells
- 3. Pulpitis: inflammatory process affecting the coronal and radicular
- 4. Pulp Necrosis: All pulp tissue is necrotic

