1.20 Study Hypotheses

The calculations are based on a comparison of the test results and "true" disease status. The sensitivity, specificity, and positive and negative predictive values of heat and cold application and electrical pulp tests will be calculated. Teeth are grouped into two categories, healthy, true disease (irreversible pulpitis and necrosis). A perfect diagnostic test would always be positive in the presence of disease and negative in the absence of disease. Therefore, sensitivity, specificity, and positive and negative predictive value have been developed to characterize test accuracy and to compute the benefits of test usage. In addition to that, clinical measurements of the extracted teeth will be compared with identification of the true disease by histological evaluation for the pulp status.

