1.22 Final Analysis Plan

To compare accuracy of pulp vitality between traditional tooth vitality testing (Cold and EPT) to pulse oximeter reading to determine if the pulse oximeter is a reliable indicator of tooth vitality. We will analyze the relationships between these clinical readings using Pearson correlations and/or Chi Square tests. We will evaluate repeatability of the measurements within a tooth for the pulse oximeter using Bland-Altman plots, intraclass correlation coefficients (ICCs), and the percentage of repeat measurements within +/- 0.5 mm along with a 95% confidence interval for the percentage. Pulse oximeter reading will be compared against the gold standard (Cold and EPT) assessment using paired t-tests, 95% confidence intervals for the difference from the gold standard with a 95% confidence interval. The clinical pulpal status will be compared to the histological status for the difference using ANOVA and compared for the percentage of measurements with +/- gold standard visual assessment of the pulp status using McNemar's tests.

SOURCE DOCUMENTS AND ACCESS TO SOURCE DATA/DOCUMENTS

Study staff will maintain appropriate dental and research records for this study. Study staff will permit authorized representative and regulatory agencies to examine (and when required by applicable law, to copy) research records for the purposes of quality assurance reviews, audits and evaluation of the study safety, progress and data validity.

QUALITY CONTROL AND QUALITY ASSURANCE

Quality control will be continually monitored by periodic (semi-annual) reviews of the protocol and procedures used in the study. All questionnaire data is reviewed on the day of the participant visit for completeness. De-identified data is monitored after collection for various points of quality assurance.

ETHICS/PROTECTION OF HUMAN SUBJECTS:

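### Section 1.22 compares clinical status with histology only by ANOVA and McNemar's test, neither of which measures accuracy, and no planned analysis gives the pulse oximeter's accuracy against histology

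*Combined protocol and SAP*

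**What the plan says.** Section 1.22 opens with an accuracy goal: "To compare accuracy of pulp vitality between traditional tooth vitality testing (Cold and EPT) to pulse oximeter reading". For histology it then names two methods. The first is "The clinical pulpal status will be compared to the histological status for the difference using ANOVA"; the second is that status is "compared for the percentage of measurements with +/- gold standard visual assessment of the pulp status using McNemar's tests". It names no sensitivity, specificity, AUC, kappa or percentage agreement against histology. The sentence before this one calls Cold and EPT the gold standard, so the term has two meanings within the section.

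Section 1.20 does plan accuracy measures: "The sensitivity, specificity, and positive and negative predictive values of heat and cold application and electrical pulp tests will be calculated". The pulse oximeter is not in that list. Section 1.20 then adds histology as a further comparison without naming a statistic: "In addition to that, clinical measurements of the extracted teeth will be compared with identification of the true disease by histological evaluation". It also sets the disease grouping: "Teeth are grouped into two categories, healthy, true disease (irreversible pulpitis and necrosis".

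Section 1.15 gives four histology classes. One of them, "Transitional Stage: Intact pulp with scattered inflammatory cells", is not assigned to either of the two groups in 1.20. Section 1.5 lists histology among the exploratory outcomes. Aim 4 asks whether pulpal blood flow reliably indicates vitality, drawing on Aims 1 to 3, and Aim 3 is the histology.

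**The concern.** Whether a diagnostic test can be trusted depends on how often it is wrong, separately in diseased and in healthy teeth. McNemar's test of a single test against its reference uses only the two discordant cells and asks whether they are balanced. Correct calls do not enter the statistic. A test with many errors that cancel looks the same as a test with few errors that cancel, and a test with few errors in one direction looks worse than either.

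The ANOVA wording defines neither outcome nor factor. If it compares the mean code for clinical status with the mean code for histological status, it has the same blind spot.

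This is the only comparison in 1.22 tied to the actual state of the pulp. If its p-values were taken as evidence on reliability, they could favour an uninformative device or count against a useful one. Aim 4 would be left without an estimate of the oximeter's accuracy.

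**Working it through.** The plan has no figure to reproduce. Section 1.21 gives 35 completers with no alpha, power, prevalence or precision target.

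**Inputs**
- Teeth with histology, N: not stated. Section 1.6 requires at least one scheduled extraction. Assumed 35, 60 and 100.
- Proportion diseased, π: not stated. Assumed 0.30, 0.50 and 0.70.
- Exact McNemar test, two-sided 5%: assumed, because 1.22 uses 95% intervals.
- Sensitivity (Se) and specificity (Sp): illustrative.
- Teeth treated as independent.

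**Formulas**
- Probability of a false positive: FP = (1 − π)(1 − Sp). Probability of a false negative: FN = π(1 − Se).
- The number of discordant teeth is binomial (N, FP + FN). Given that number, false positives are binomial with probability FP/(FP + FN).
- The chance of p < 0.05 is the sum of these probabilities over all tables in which the exact test rejects.
- Agreement = π·Se + (1 − π)·Sp. Kappa = (agreement − chance agreement)/(1 − chance agreement).

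**Uninformative test with the same positive rate as histology.** Here Se = π and Sp = 1 − π, so FP = FN = π(1 − π) and kappa is 0. At π = 0.30, FP = FN = 0.21 and agreement is 0.58. McNemar rejects in 2.7%, 3.0% and 3.5% of studies with 35, 60 and 100 teeth. At π = 0.50 the figures are 3.0%, 3.1% and 3.7%. The test is therefore found not different from histology in 96% to 97% of studies.

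**Useful test, Se = 0.95 and Sp = 0.80**

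| π | FP | FN | Agreement | Kappa | Rejects, N = 35 | N = 60 | N = 100 |
|---|---|---|---|---|---|---|---|
| 0.30 | 0.140 | 0.015 | 0.845 | 0.67 | 25.6% | 63.5% | 90.5% |
| 0.50 | 0.100 | 0.025 | 0.875 | 0.75 | 6.7% | 23.4% | 47.6% |
| 0.70 | 0.060 | 0.035 | 0.905 | 0.77 | 0.6% | 2.9% | 6.7% |

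Se and Sp are the same in every row. What drives the rejection rate is the imbalance between FP and FN.

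**Three tables of 35 teeth** (true positive / false positive / false negative / true negative; 95% Clopper-Pearson intervals)

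| Table | Se | Sp | Kappa | McNemar p |
|---|---|---|---|---|
| 8/9/9/9 | 0.47 (0.23–0.72) | 0.50 (0.26–0.74) | −0.03 | 1.00 |
| 15/2/2/16 | 0.88 (0.64–0.99) | 0.89 (0.65–0.99) | 0.77 | 1.00 |
| 17/6/0/12 | 1.00 (0.81–1.00) | 0.67 (0.41–0.87) | 0.66 | 2 × (1/2)^6 = 0.031 |

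McNemar gives the worthless table and the good balanced table the same p-value, and flags only the third. Sensitivity and specificity separate the first table from the other two.

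**ANOVA, two readings**
- Method as the factor (clinical code against histology code, repeated measures): p = 1.00 for 8/9/9/9 and p = 0.012 for 17/6/0/12. This is the same fault as McNemar's.
- Results compared across histology groups: p = 0.87 for 8/9/9/9 and p < 0.001 for 17/6/0/12. This detects association. It does not give accuracy: a mean difference of 0.8 SD between two groups has 66% power with 17.5 teeth per group and 98% with 50 per group, yet AUC = Φ(0.8/√2) = 0.71 and, at the midpoint cut-off, Se = Sp = Φ(0.4) = 0.66.

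**The case against.** Several points on the other side have force.

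- A reader might infer that ANOVA has no valid use here because both statuses are categories. The documents do not support that. Section 1.5 counts numeric oximeter readings among the measurements of pulpal status, and 1.20 speaks of clinical measurements being compared with histology. One-way ANOVA of readings across the four classes is a legitimate test of association, and an uninformative reading would usually show none. What stands is that the outcome and factor are undefined, and that neither reading yields accuracy.
- A reader might infer that the plan contains no accuracy measures. It does: 1.20 lists four for heat, cold and EPT. The gap is narrower. The oximeter is missing from that list, and the histology comparison is added with no statistic named.
- A reader might infer that any test wrong half the time passes McNemar's test. That fails when the false-positive and false-negative rates differ. With Se = Sp = 0.50 and π = 0.30, FP is 0.35 against FN 0.15, and the test rejects in 31%, 53% and 79% of studies with 35, 60 and 100 teeth.
- A reader might infer that a good test will usually be rejected. That depends on prevalence, as the table shows. A test with 90% sensitivity and specificity at π = 0.30 is rejected in only 1%, 6% and 15%.
- The McNemar sentence is unclear. If it meant comparing the percentages correct of two tests, the method would be sound. The text does not say so.
- No rule in the plan says that a non-significant result means equivalence to histology. That reading is a risk left open by the wording, not a stated decision.
- Histology is exploratory; the primary outcome is the correlation between subjective and objective measurements. This limits the severity, although Aim 4 still depends on histology.

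**Conclusion.** The point holds in this form: the histology comparison in 1.22 does not measure accuracy, and the oximeter's accuracy against histology is not planned anywhere. An uninformative test with matching positive rate escapes McNemar's test in about 97% of studies at any of the tooth numbers considered. The opposite error, a useful test found different, ranges from 1% to 90% for the 95%/80% test across the assumed prevalences and tooth numbers, and should not be quoted from a single scenario. Prevalence, number of histology teeth, test performance and alpha are all assumptions, and clustering within participants was ignored in the calculation. Severity is should-fix, because histology is an exploratory outcome.

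**What to change.** In 1.22:

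1. Replace the McNemar test of clinical status against histology with the sensitivity and specificity of each test, expressly including the pulse oximeter, against dichotomised histology in extracted teeth. Give 95% intervals that allow for clustering of teeth within participant.
2. Fix in advance which group the transitional stage joins, and add a sensitivity analysis with the other grouping.
3. Report ROC and AUC with a 95% interval for the continuous oximeter reading.
4. Do not run ANOVA on status codes. It may stay as a descriptive comparison of numeric readings across the four histology classes.
5. Keep McNemar's test, in a participant-clustered form, only for comparing correct calls by the oximeter with those by Cold/EPT within histologically diseased teeth and, separately, within non-diseased teeth.

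No new data are needed. The cost is modest extra analysis, and the need either to pre-specify an oximeter cut-off, which the documents do not define, or to rely on the AUC.

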1.23 Ethical Standard

The investigator will ensure that this study is conducted in full conformity with the principles set forth in The Belmont Report: Ethical Principles and Guidelines for the Protection of Human Subjects of Research, as drafted by the US National Commission for the Protection of Human Subjects of Biomedical and Behavioral Research (April 18, 1979) and codified in 45 CFR Part 46 and by the Institutional Review Board requirements of the University of Michigan.

1.24 Institutional Review Board

The protocol, informed consent form(s), recruitment materials and all participant materials have been submitted to the IRB for review and approval. Any amendment to the protocol will require review and approval by the IRB before the changes are implemented in the study. Please see accompanying IRB application and letters of approval, and Informed Consent document.

1.25 Informed Consent Process

Informed consent is a process that is initiated prior to the individual agreeing to participate in the study and continues throughout study participation. Extensive discussion of risks and possible benefits of study participation will be provided to participants and their families, if applicable. A consent form describing in detail the study procedures and risks will be given to the participant. Consent forms will be IRB-approved, and the participant is required to read and review the document or have the document read to him or her. The principle investigator will explain the research study to the participant and answer any questions that may arise. The participant will sign the informed consent document prior to any study-related assessments or procedures. Participants will be given the opportunity to discuss the study with their surrogates or think about it prior to agreeing to participate. They may withdraw consent at any time throughout the course of the study. A copy of the signed informed consent document will be protected by emphasizing to them that the quality of their clinical care will not be adversely affected if they decline to participate in this study.

The consent process will be documented in the clinical or research record.

1.26 Exclusion of Women, Minorities, and Children (Special Populations)

Children below the age of 18 and cognitively impaired adults are excluded from the current study.

1.27 **Participant Confidentiality**

Participant confidentiality is strictly held in trust by the investigators, and study staff. This confidentiality is extended to cover testing of biological samples in addition to any study information relating to participants. The study protocol, documentation, data, and all other information generated will be held in strict confidence.

1.28 Future Use of Stored Specimens and Other Identifiable Data

The de-identified extracted teeth will be transferred for histological evaluation on the same day to the pathology laboratory at the school of dentistry.

DATA HANDLING AND RECORD KEEPING

Several measures have been taken to reduce the risk of breach of confidentiality. These include training of study team members, electronic and physical security measures for data capture and storage, and collecting a minimum of identifiable information for each individual. Breach of confidentiality will be considered a "definitely related" Serious Adverse Event. As such, it will be reported to the University of Michigan IRB within 7 days of occurrence, and a remediation plan will be put in place immediately.

1.29 Data Management Responsibilities

Data collection and accurate documentation are the responsibility of the principal investigator and study staff under the supervision of the principal investigator. All source documents and laboratory reports must be reviewed by the principal investigator and/or the study team and/or data entry staff, who will ensure that they are accurate and complete. Unanticipated problems must be reviewed by the investigator or designee.

1.30 Data Capture Methods

Data will be kept confidential, in part, by assigning each participant an ID number. This number will be used to keep track of each individual's data. Participant names will never be collected or stored with research data. Paper copies of the data from questionnaires and radiographic copy of each participant will be stored in a locked file cabinet in a locked office. Paper copies of the consent document and the payment processing forms (i.e. those containing subject names) will be stored in a separate locked filing cabinet away from the data. The PI (or a designee) will retain the keys to access these files.

Participants will complete paper-based questionnaires; no electronic survey completion will occur. Data will be verified and checked for completeness and initialed by the principle investigator prior to the completion of the visit. All data will be entered into a research database, REDCap and/or excel.

Study data will be collected and may be managed using an electronic data capture tools hosted at University of Michigan. REDCap (Research Electronic Data Capture) is a secure, web-based application designed to support data capture for research studies, providing: 1) an intuitive interface for validated data entry; 2) audit trails for tracking data manipulation and export procedures; 3) automated export procedures for seamless data downloads to common statistical packages; and 4) procedures for importing data from external sources.

1.31 **Types of Data**

Outcome measure data of cold testing, EPT, percussion, palpation testing and pulse oximeter reading will be collected in the study. Extracted teeth that meet the inclusion criteria will be also collected for histological evaluation.

1.32 Schedule and Content of Reports

De-identification of data occurs with the generation of study documents, including the assignment of a unique research ID to each participant's data.

Please indicate the extent to which	Not at all (1)	A small extent (2)	Moderate extent (3)	A large extent (4)	Complete extent (5)
11. the tooth where you have the pain from feels like it is sticking out a little:					
	Full extent (5)	A large extent (4)	Moderate extent (3)	A small extent (2)	Not at all (1)
12. Please indicate the extent to which you have had difficulties with sleeping:					
13. Which of the following word(s), if any, would pain?	you use to de	scribe your cu	urrent	Yes (1)	No (0)
			Exhausting		
		Elec	tric shocks		
			Pulling		
			Numb		

14. What other word(s), if any, would you use to describe your current pain? Please write in the space

below:

Subject ID #:	
Visit#:	
Visit Date:	

Fibromyalgia Survey Questionnaire (FSQ)

1. Please indicate below if you have had pain or tenderness over the past 7 days in each of the areas listed below.

Please make an X if you have had pain or tenderness. Be sure to mark both right and left sides separately.

2. Using the following scale, indicate for each item the level of severity over the past week by checking the appropriate box.

	No Problem	Slight or mild	Moderate	Severe
a. Fatigue		\Box_1	\square_2	\square_3
b. Trouble thinking or remembering	\square_0	\square_1	\square_2	\square_3
c. Waking up tired (unrefreshed)		\Box_1	\square_2	\square_3

3. During the past 6 months have you had any of the following symptoms?

a. Pain or cramps in lower abdomen	\Box_1 Yes	\square_0 No
b. Depression	\Box_1 Yes	\square_0 No
c. Headache	\Box_1 Yes	\square_0 No

4. Overall, were the symptoms listed in questions 1-3 above, generally present for at least 3 months?

 \Box_1 Yes \Box_0 No

5. Do you have a disorder that would otherwise explain the pain?

 \Box_1 Yes \Box_0 No

FORMS

Assessment of Tooth	MEASUREMENT	ID Number	FORM
Vitality Using Pulse	READING		2
Oximeter	Date:		Examiner:

SPECIMENS	
How many teeth are selected?	
How many of them are treatment planned for extraction?	

MEASURMENTS		
Tooth #:	LOCATION	READINGS
Endo Ice (Cold)		
EPT		
Pulse Ox		
Laser Doppler Flowmeter		
Percussion		
Palpation		

MEASURMENTS		
Tooth #	LOCATION	READING
Endo Ice (Cold)		
EPT		
Pulse Ox		

Laser Doppler Flowmeter	
Percussion	
Palpation	

MEASURMENTS		
Tooth #	LOCATION	READING
Endo Ice (Cold)		
EPT		
Pulse Ox		
Laser Doppler Flowmeter		
Percussion		
Palpation		

MEASURMENTS		
Tooth #	LOCATION	READING
Endo Ice (Cold)		
EPT		
Pulse Ox		
Laser Doppler Flowmeter		
Percussion		
Palpation		

Assessment of Tooth Vitality Using Pulse Oximeter	Documentation of Specimens Collection	ID Number	FORM 3
	Date:		Name of Person Recording the Specimen:

SPECIMENS		
Extracted tooth/teeth was/were collected	YES	NO
How many teeth were extracted?		
IF NOT collected, why?		
Date of tooth collection		
Are the extracted tooth/teeth placed in formalin-containing bottle?	YES	NO
Are the extracted tooth/teeth transferred to the School of Dentistry laboratory for further analysis?	YES	NO

ADVERSE EVENTS		
Have there been any adverse events?		
(if "Yes" complete AE form 2 and provide details in "Comments"	YES	NO
section)		

COMMENTS
